5.6 Method for handling Outliers

At the data entry stage, ranges are set for key outcome variables as collected in the questionnaires. The data entry screens and databases will be created in reference to the questionnaire so the range checks are consistent with what was expected. For example, variable to record hypertension will be coded as 1 if "yes" and 0 if "no". Any values, besides these two, will be considered out of range. For continuous variables, it is a challenge to determine outliers. For example, for blood pressure and blood glucose levels, the team will have to determine acceptable levels, and as such these cannot easily be set at data entry stage.

If a value is flagged as being out of range the questionnaire is returned to the field team. If there is no apparent error, then the out-of-range variable is considered by two senior members of the research team and a decision is made in each case on whether the value is plausible (for example a known diabetic with an out-of-range blood glucose), If the value was felt to be implausible the variable is being entered as 'missing'.

In terms of methods in analysis for handling this, the approaches we will adopt will be to work with and without outlier variables; and also adopting multiple imputation procedures able to cater for clustering.

5.7 Derived and Computed Variables

This section is directly linked to objectives of the study (Section 2 and, specifically, section 2.2 on outcomes). Two variables we will need for many of the outcomes listed below are mean systolic hypertension and mean diastolic hypertension. Each of these will be calculated by discarding the first of the three measures taken (because the first one is usually artificially high due to the person's reaction to having their blood pressure measured), and then calculating the mean of the second and third measures. The same goes for mean pulse.

The **primary outcome** (as outlined in Table 2) requires us to calculate 'the percentage of people in the population who have elevated blood pressure that is combined with other factors resulting in a risk profile that indicates moderate or greater added risk of cardiovascular disease'. Appendix C (section 15.3) shows STATA commands for generating this primary outcome variable.

We have listed six secondary outcomes (Section 2.2.2). The first of these is a change in the **proportion of the population with undiagnosed hypertension.** We will need a new binary variable for undiagnosed hypertension. This should be calculated using a combination of mean systolic and diastolic BP plus the answers to questions 2 and 3 – (on the questionnaire). Thus, someone with undiagnosed hypertension will have answered "No" to question 2 and question 3 below, and will have EITHER a mean systolic pressure equal to or greater than 140 OR a mean diastolic pressure equal to or greater than 90 (or both). Question 2 states that "*Have you ever been told by a doctor, nurse or other health worker that you have raised blood pressure or hypertension?*" Question 3 is "*Have you received any drugs for high blood pressure prescribed by a doctor, nurse or other health worker in the last two weeks?*"

The second secondary outcome checks for **change in the proportion of the population reporting they had had their blood pressure measured**. This will be derived from Question 4 – "Have you ever had your blood pressure measured by a *doctor, nurse or other health workers?*" The third secondary objective is on **change in the proportion of the population reporting that they are using medication for hypertension.** Derived from Question 3 – "Have you received any drugs for high blood pressure prescribed by a doctor, nurse or other health worker in the last two weeks?. These two are direct variables from the questionnaire and do not need any further computation. For the primary analysis of this outcome, only those who name specific drugs will be categorized as being prescribed drugs for high blood pressure.

The fourth is change in the proportion of the population at different levels of bloodpressure-related cardiovascular risk by age group and sex. In this case we will also need **blood-pressure-related cardiovascular risk** divided into the different levels of no added risk, low added risk, moderate added risk and high added risk (see Table 2).

The secondary objectives under section 2.2.2, e and f (restated below) do not need any additional computations, and will be derived from clinic link data. These two outcomes are:

- e) Change in the proportion of people in the population recorded as having attended a clinic in the last year.
- f) Retention in care of people with diagnosed hypertension defined by the proportion of appointments kept during the study period.

Note that the clinic link data will provide information on the proportion of people recorded as having attended a clinic in the last year, rather than, as originally stated, reporting they had attended.

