1.4 Changes from planned analysis in the protocol

No changes are planned from the analysis described in the protocol.

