2.2 Outcome Measures

2.2.1 Primary Outcome

A population level measure of hypertension control will be derived from cross-sectional surveys carried out before and after the intervention. This primary outcome will be the change between the two surveys in the percentage of people in the population who have elevated blood pressure that is combined with other factors resulting in a risk profile that indicates moderate or greater added risk of cardiovascular disease. More detailed definitions of outcomes are described in section 5.7.

2.2.2 Secondary Outcomes

- a) Change in proportion of the population with undiagnosed hypertension (see table 10 in the appendix)
- b) Change in the proportion of the population reporting they had had their blood pressure measured (see table 10 in the appendix),
- c) Change in the proportion of the population reporting that they are using medication for hypertension (see table 10 in the appendix)
- d) Change in the proportion of the population at different levels of blood-pressurerelated cardiovascular risk by age group and sex (see tables 5, 6, 7, 8 and 9 in the appendix)
- e) Change in the proportion of people in the population reporting that they have attended a clinic in the last year (see table 10 in the appendix)
- f) Retention in care of people with diagnosed hypertension defined by the proportion of appointments kept during the study period (see table 11 in the appendix)

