4.5 Clinic link data

During the intervention period, a study data clerk asked every chronic patient arriving at both control and intervention clinics, for consent to collect data from their clinical file and to link it to their census record. Following consent, all visits for that patient were then recorded.

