cardiovascul	proportion(n))		proportion	1(11)		statistic assessing
ar risk							difference
	Baseline	End	Within	Baseline	End	Within	between cluster
	Prop (n)	Prop (n)	cluster	Prop (n)	Prop (n)	cluster	change and p-
			change			change	value
			and p-			and p-	Value
			value			value	
No or low							
risk							
No risk							
Low risk							
Moderate or							
higher risk							
Moderate							
risk							
High risk							
Very high							
risk							

Repeat for men and women

	Control proportion((n)		Intervention proportion		Statistical Test statistic assessing	
	Baseline Prop (n)	End Prop (n)	Within cluster change and p- value	Baseline Prop (n)	End Prop (n)	Within cluster change and p- value	difference between cluster change and p- value
People with moderate or higher risk***							
Undiagnosed hypertension							
Self-reported blood pressure measured							
Self-reported using medication for hypertension							
Self-reported attended a clinic in the last year.							

Table 10: Changes in hypertension risk, blood pressure, medication and attendance within clusters

Variable		Cont	rol clinic	S		Interv	Intervention clinics		
		1	2	3	4	1	2	3	4
Total number of	of visits								
Number of pat	ients								
Sex	Male								
	Female								
Age	Mean age								
Patient	Visit with 3								
attendance	days of								
(Proportion	appointment								
of visits	Visit NOT								
attended	within 3 days								
within 3 or	of								
less days of	appointment								
appointment	No								
date)	appointment								
Given full set	Yes								
of medication	No								

Table 11: Clinic link record of number of visits by sex, age, patient attendance and availability of medication over 4 time periods (each 5 months long)

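### Section 5.7 takes the change in clinic attendance (secondary outcome e) from records that have no baseline, and the table for retention (outcome f) leaves out appointments never followed by a visit

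*SAP*

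**What the plan says.** **Outcome e.** SAP section 2.2.2 defines it as "Change in the proportion of people in the population reporting that they have attended a clinic in the last year" and sends it to Table 10 in the appendix. The matching row of that table reads "Self-reported attended a clinic in the last year", with baseline, end and within-cluster change columns for each arm. Section 5.7 restates the outcome as "Change in the proportion of people in the population recorded as having attended a clinic in the last year". It says openly that recorded attendance replaces reported attendance, and that outcomes e and f "do not need any additional computations, and will be derived from clinic link data".

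Section 4.5 describes how those data arose: "During the intervention period, a study data clerk asked every chronic patient arriving at both control and intervention clinics", to obtain consent, after which that patient's visits were recorded. Section 5.8 puts the span at about 18 months.

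**Outcome f.** Section 2.2.2 defines it as "Retention in care of people with diagnosed hypertension defined by the proportion of appointments kept during the study period". Sections 5.7 and 5.8 agree, and 2.2.2 sends it to Table 11. The title of that table begins "Clinic link record of number of visits by sex, age, patient attendance and availability of medication over 4 time periods", each of 5 months. Its attendance rows sort visits into three kinds: within 3 days of the appointment, not within 3 days, and no appointment.

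**The concern.** For outcome e, a change needs a measurement before the intervention, and the source named in 5.7 appears to have none. Section 7.1 says that secondary outcomes are analysed like the primary, and section 6.3 compares baseline with follow-up within each group. Link data cannot feed that analysis. An analyst holding this SAP would have two definitions of e, one of which cannot be computed, and could choose between them after seeing the data.

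For outcome f, a retention measure has to register the people who stop coming. A table whose unit is the visit made cannot show an appointment that produced no visit. Table 11 also has no count of appointments due and no restriction to people with diagnosed hypertension, although section 4.5 enrols chronic patients generally. Keeping people in care is part of what the lay health workers are there to do, so the table is weakest where an effect would be looked for.

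**Working it through.** The SAP gives no figure for either outcome, so there is nothing to reproduce. The check for e is calendar arithmetic. The check for f compares two denominators, using assumed counts.

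**Outcome e**

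Inputs:
- look-back period in the definition: 12 months (2.2.2, 5.7)
- intervention: from February 2014, for 21 months (4.3)
- link record: about 18 months (5.8); Table 11 implies 4 × 5 = 20 months; collection within the intervention period (4.5) allows at most 21
- link record before February 2014: none described, so 0 months

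A change between two separate last-year windows needs 2 × 12 = 24 months, with the first 12 before the intervention.
- 18-month record: 24 − 18 = 6 months short
- 20-month record: 24 − 20 = 4 months short
- 21-month record: 24 − 21 = 3 months short
- months available for the baseline window: 0 of 12 in every case

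The total shortfall is secondary. The missing window lies before the start, so a longer record at the end would not supply it.

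The surveys do hold the information. Section 4.1 lists clinic use over the previous 12 months among the baseline items, and section 4.2 says the follow-up survey collects the same data. That is what Table 10 is laid out to show.

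**Outcome f**

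Let K be appointments kept within 3 days, L those followed by a late visit, and N those never followed by a visit. The defined outcome is K / (K + L + N). Table 11 gives K / (K + L). Assume 100 appointments due and K = 60, with each late return counted as one visit not within 3 days and visits without an appointment set aside:

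| L (late) | N (never) | Defined outcome | Table 11 |
|---|---|---|---|
| 40 | 0 | 60/100 = 60% | 60/100 = 60% |
| 30 | 10 | 60/100 = 60% | 60/90 = 67% |
| 15 | 25 | 60/100 = 60% | 60/75 = 80% |
| 0 | 40 | 60/100 = 60% | 60/60 = 100% |

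The second and third rows can be read as two arms. Both keep 60% of appointments, yet the arm that loses more patients altogether looks about 13 points better (80% − 67%).

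The size also depends on how appointments are issued, which the SAP does not state. Assume 10 patients with a schedule of 6 appointments each, 3 of whom stop after 2 visits, and all visits on time. Visits made are 7 × 6 + 3 × 2 = 48, so Table 11 shows 48/48 = 100%.
- If all 6 dates count for everyone, retention is 48/60 = 80%.
- If each date is issued at the previous visit, each drop-out has only 3 issued dates. The denominator is 7 × 6 + 3 × 3 = 51, and retention is 48/51 = 94%.

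The direction is the same, but the gap is 20 points in one case and 6 in the other.

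**The case against.** The strongest reply is that the move to recorded attendance in 5.7 was deliberate and declared, and that the remaining faults are leftover wording and the layout of a dummy table. Much of this stands. Keeping recorded attendance and dropping the word change would also be coherent for e. For f, the definition is the same wherever it appears.

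Several stronger readings are tempting, and the SAP does not support them:
- **That link data cannot deliver f.** Table 11 places visits relative to an appointment date, so dates appear to be held for at least some visits. If each record holds the next date, appointments due can be rebuilt. The SAP does not say whether it does.
- **That e without a baseline would be uncontrolled.** Section 4.5 covers control and intervention clinics alike. A comparison over one window would have concurrent randomised controls and would lack only baseline adjustment.
- **That section 1.4 is breached.** It says "No changes are planned from the analysis described in the protocol". The protocol is not at hand, and the wording that 5.7 departs from could be the protocol's or that of section 2.2.2.
- **That acute attenders are excluded.** Section 4.5 speaks of chronic patients, while 5.8 speaks of consenting attenders in general. This is an ambiguity to clear up.
- **That Table 11 overstates retention by a known amount.** Patients who return late do count against the clinic. If every missed appointment ends in a late visit, there is no overstatement.

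What the reply does not answer is that e is still called a change and has no baseline in its named source, and that f is sent to a table without its denominator.

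**Conclusion.** The point holds for both outcomes, more firmly for e.

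The change in e cannot be computed from the source that 5.7 names: 0 of the 12 baseline months exist in the record as described. Section 5.7 also contradicts 2.2.2 and Table 10. This rests only on the SAP's own dates and its account of when link data were collected.

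For f, the fault lies in Table 11 and in the claim that nothing further needs computing. Retention can be overstated by an amount that depends on the unknown mix of late returns and no-shows, and on how appointments were issued. The range of 60% to 100% for a true 60% is an assumed illustration and does not estimate what happened in this trial.

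Both are secondary outcomes. The primary outcome comes from the surveys alone and is unaffected. The corrections should be made before analysis.

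**What to change.** **Outcome e.** In 5.7, derive it from the survey item on clinic use in the last 12 months, asked in both surveys, as Table 10 already shows. Report link-data attendance separately, as a between-arm comparison over a stated 12-month window with a stated population denominator, and do not call it a change. State whether it covers only chronic patients (4.5) or all consenting attenders (5.8). The cost is wording, since the survey data are planned at both time points. The drawback is that e stays self-reported.

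**Outcome f.** In 5.7 and Table 11:
- restrict to people with diagnosed hypertension
- take as denominator all issued appointments falling due within the link-data period, censored at death or out-migration
- count an appointment with no visit as not kept
- state the window that counts as kept and how visits without an appointment are handled
- give one link-data period in place of the 18, 20 and 21 months now implied
- state that the measure depends on the link record holding the next appointment date

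Delete the statement in 5.7 that no additional computations are needed. The cost is a short derivation and a reworked Table 11. If the next appointment date was not recorded, the SAP should say that f cannot be computed as defined and should label the Table 11 figure as timeliness of visits made.

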5.8 Description of clinic link data

The clinic link data will provide information on attendance at any one of the eight trial clinics over a period of around 18 months by residents of the Agincourt research census site. Consenting individuals attending a clinic are identified in real time on the census data base (using fuzzy matching) by trained data clerks posted in all the clinics. Information about all clinic attendances of identified individuals, including diagnosis and medication prescribed, is recorded. These linked data will enable us to compute by clinic:

- The proportion of people in the population recorded as having attended each clinic in the last year
- Proportion of appointments kept during the study period by those individuals with a diagnosis of hypertension.

The clinic link data also provide the potential to describe socio-demographic differences between those who attend and those who do not attend the clinics – an investigation of association with secondary outcomes (bullet points above) using the logistic regression models, taking into account the clustering in the data.

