Last year we went to find out what is happening in the clinics and we did a population based survey of blood pressure. When the LHWs are in the clinic we will evaluate their work, and then after two years we will go back to the community and do another population based survey to see if their blood pressures have changed. [name] and his team's role is to evaluate the project while [name] will work to develop the LHW intervention

Lay health worker programme – [name]

[name] described what the lay health worker will do in the clinic. Duties might differ between clinics as clinics are different (size, number of staff, business etc). Will workshop with clinic staff to decide how the lay health workers should be working with the clinic staff. [name]'s role in the programme is to develop the work of the LHW in the clinic.

The randomisation process – [name]

[name] explained how we are going to randomise the clinics.

- 1. Reminder that this is research
- 2. We will look at each clinic separately so that we can tell why the programme worked well in one clinic but not in the other if this is the case. This is especially true for this project as the LHW programmes will be different in each clinic.
- 3. We did not want to just decide in the office which clinic to chose, so we are doing it randomly and publicly. Every clinic should have an equal chance to be selected as an intervention clinic.
- 4. Described difference between control and intervention clinics.
- 5. Showed the eight pieces of paper with the clinic names on them
- 6. Showed the 8 unmarked envelopes
- 7. Put one clinic name into its own envelope
- 8. Put all the envelopes into the box
- 9. Two or three people will come and shake the box
- 10. Then we will get 7 people to come up and each chose an envelope.
- 11. First, third, fifth and seventh clinics taken out will be intervention
- 12. Second, fourth, sixth and eight clinics taken out will be control

Everyone agreed that it is a fair process before we started.

- 1. [name] put all the names into envelopes in front of everyone
- 2. All envelopes were put in a box
- 3. A volunteer came up to shake the box
- 4. Audience suggested we fold the envelopes so that they moved more easily in the box
- 5. We opened the box and folded the envelopes smaller
- 6. Second person came and shook the box
- 7. First person chose -
- 8. Another person shook the box

- 9. Second person chose -
- 10. Another person shook
- 11. Third person chose -

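### Secondary outcome (e) takes clinic attendance in the whole population from a record that, by section 4.5, covers consenting chronic patients

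*SAP*

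**What the plan says.** **Who is recorded.** Section 4.5 describes how data were gathered while the intervention ran: "a study data clerk asked every chronic patient arriving at both control and intervention clinics, for consent to collect data from their clinical file". The same consent covered linkage with the census. On what happened next, the section adds: "Following consent, all visits for that patient were then recorded".

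**How section 5.8 words it.** "Consenting individuals attending a clinic are identified in real time on the census data base (using fuzzy matching"). The word chronic does not appear in this description.

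**What is computed.** By clinic, section 5.8 derives "The proportion of people in the population recorded as having attended each clinic in the last year". Section 5.7 makes the link data the source of outcome (e), "Change in the proportion of people in the population recorded as having attended a clinic in the last year", says no further computation is needed, and notes that this measures recorded attendance "rather than, as originally stated, reporting they had attended".

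**Further use.** Section 5.8 sees potential in the same data to "describe socio-demographic differences between those who attend and those who do not attend the clinics", using logistic regression.

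**What other sections say about (e).** Section 2.2.2(e) and dummy Table 10 still define it as self-reported attendance. Section 4.1 lists use of primary care clinics in the last 12 months among the survey questions, and section 4.2 repeats the same data collection at follow-up.

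**The concern.** The numerator and denominator describe different groups. The denominator is the population. By section 4.5, the numerator can contain only people who were chronic patients, agreed to take part and were matched to the census. A resident who came to the clinic with an acute illness did attend, but does not count.

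This has two consequences. First, the level is too low, so the figure is not the attendance proportion that outcome (e) names. Second, the figure can move without any change in attendance. Someone who already visits the clinic for other reasons and is then diagnosed with hypertension becomes a chronic patient and can be recorded. Section 3.1 states that the trial aims to increase the share of the population under active management for hypertension, so such moves may be more frequent in the intervention arm. Access to care is part of the primary objective (section 2.1.1), and a rise of this kind could be read as better access.

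The attender versus non-attender comparison in section 5.8 has the same weakness: an unrecorded resident is not necessarily a non-attender.

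**Working it through.** The SAP gives no attendance rate, chronic share, consent rate or match rate, so there is no stated figure to reproduce. The main check sets the sections side by side.

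| Resident | Attended a clinic? | In the denominator (5.7, 5.8)? | Can enter the numerator (4.5)? |
|---|---|---|---|
| Chronic patient, consents, matched | Yes | Yes | Yes |
| Chronic patient, refuses or not matched | Yes | Yes | No |
| Attends only for acute problems | Yes | Yes | No |
| Does not attend | No | Yes | No |

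Rows two and three are attenders who end up with the non-attenders. No section removes them from the denominator or adds them to the numerator.

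**Illustration. Every rate below is an assumption.**

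Let A be true attendance, c the share of attenders who are chronic patients, and q the consent and match rate combined. Then recorded attendance = A × c × q, and the share of true attenders not recorded = 1 − c × q.

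Ranges: A = 50-70%, equal in both arms; c = 30-50% in control; q = 80-95%.

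- Lowest recorded value: 0.50 × 0.30 × 0.80 = 12.0%.
- Highest recorded value: 0.70 × 0.50 × 0.95 = 33.25%.
- Attenders not recorded: from 1 − 0.50 × 0.95 = 52.5% to 1 − 0.30 × 0.80 = 76%.

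Now let c in the intervention arm exceed c in control by d, with A and q equal in both arms. The spurious difference is A × d × q.

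- d = 5 points: 0.50 × 0.05 × 0.80 = 2.0 points to 0.70 × 0.05 × 0.95 = 3.3 points.
- d = 10 points: 4.0 points to 0.70 × 0.10 × 0.95 = 6.65 points.
- d = 0: no spurious difference.
- Example: A = 60%, c = 30% v 40%, q = 95% gives 17.1% v 22.8%, a difference of 5.7 points with no change in attendance.

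**If clerks approached all attenders**, as the wording of section 5.8 would allow, c drops out. Recorded attendance is A × q, from 0.50 × 0.80 = 40% to 0.70 × 0.95 = 66.5%, and 5-20% of attenders are missed. New diagnosis then no longer moves anyone into the numerator.

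**Time points.** Section 4.5 places collection in the intervention period, and section 5.8 gives around 18 months of data. The link record therefore has no pre-intervention value from which to form the change that (e) requires. The survey has both.

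**The case against.** The strongest reply is that section 4.5 says every chronic patient was asked and does not say that no one else was, while section 5.8 speaks of consenting individuals in general. This stands as far as it goes: the two sections must be reconciled, and if all attenders were approached only non-consent and failed matching remain. But 4.5 is the only section that states whom the clerks asked.

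Next, the outcome is labelled as recorded attendance and the switch from self-report is disclosed. That is true, but the label does not tell a reader that acute attenders could not be recorded.

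Third, a person newly entering hypertension care is partly what the trial intends, and control clinics may also diagnose more, since section 1.3 describes government initiatives that shift clinics towards chronic disease. Both points stand. Only a net excess between arms produces a spurious difference, and under-recording that is equal in both arms lowers the level without creating one. Even so, entry into chronic care is a different quantity from clinic attendance.

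Fourth, the 5.8 regression is described as a possibility, not a committed analysis. That reduces its weight but does not make the classification sound.

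A reader might also infer that each clinic's count is divided by one common population, so that the figure merely tracks clinic size, since no rule assigns non-surveyed residents to clinics and the randomisation notes say "Duties might differ between clinics as clinics are different (size, number of staff, business etc". The documents do not support this. Section 5.8 computes by clinic, section 3.1 defines the units as facilities with their surrounding catchment populations, and the remark in the notes concerns duties. What stands is that the clinic-specific denominator is not spelled out.

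**Conclusion.** The concern holds in a limited form. Read with section 4.5, the link-data version of outcome (e) understates population attendance, and it can rise when an existing attender is newly diagnosed. Whether this differs by arm, and by how much, cannot be computed from the SAP. The figures of 2.0-3.3 and 4.0-6.7 points rest on assumed rates and on a net excess of 5 or 10 points in the chronic share. It would be too strong to say that the comparison is shown to favour the intervention, because that needs an arm imbalance the documents do not quantify.

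The conclusion depends on section 4.5 being right about who was approached. If section 5.8 is the accurate description, the problem shrinks to non-consent and failed matching.

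This is a secondary outcome and the primary analysis is untouched. Outcome (f) is restricted to people with diagnosed hypertension and does not have this mismatch. The change should still be made, since the SAP already holds a better source.

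**What to change.** 1. Reconcile sections 4.5 and 5.8 on whether clerks approached chronic patients or all attenders.
2. In section 5.7, derive outcome (e) from the survey item on clinic use in the last 12 months, in line with section 2.2.2(e) and dummy Table 10. It has a population denominator, both time points and the usual-clinic assignment of section 4.4.
3. Keep the link-data figure as a descriptive measure only. Name it *residents with a recorded visit as a consenting chronic patient*, state the clinic-specific denominator and how it is formed, and say that it is not overall clinic attendance. If step 1 shows that all attenders were approached, adapt the name.
4. In the section 5.8 regression, do not class unrecorded residents as non-attenders.
5. Report consent and match rates by clinic if they were logged. The SAP is dated April 2016, after the intervention period, and describes no refusal log, so this may not be possible.

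The cost is mainly SAP wording, using survey data already planned, plus one definition for the link-data denominator. The downside is that (e) then relies on self-report, and the claim from the link data is narrower.
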